- 4. Subject who is a female and of child-bearing potential must not have a positive serum beta human chorionic gonadotropin pregnancy test at the screening visit (Visit 1) and must have a negative urine pregnancy test at the baseline visit (Visit 2) and agree to comply with any applicable contraceptive requirements of the protocol.
- 5. Subject has an ADHD-RS-5 Child, Home Version Total Score of ≥28 at baseline (Visit 2).
- 6. Subject has a Clinical Global Impression Severity of Illness (CGI-S) score ≥4 at baseline (Visit 2).
- 7. Subject functions as an age-appropriate level intellectually, as determined by the investigator.
- 8. Subject is currently not on ADHD therapy, or is not completely satisfied with any aspect of their current ADHD therapy.
- 9. Subject has lived with the same parent or LAR for at least 6 months.

Exclusion Criteria:

Subjects are excluded from the study if any of the following exclusion criteria are met:

- 1. Subject is required or anticipated to take medications that have central nervous system effects or affect performance, such as sedating antihistamines, decongestant sympathomimetics, or monoamine oxidase inhibitors. Stable use of bronchodilator inhalers is not exclusionary.
- 2. Subject has a concurrent chronic or acute illness (such as severe allergic rhinitis or an infectious process requiring antibiotics), disability, or other condition that might confound the results of safety assessments conducted in the study or that might increase risk to the subject. Similarly, the subject will be excluded if he or she has any additional condition(s) that, in the investigator's opinion, would prohibit the subject from completing the study or would not be in the best interest of the subject. The additional condition(s) would include any significant illness or unstable medical condition that could lead to difficulty complying with the protocol. Mild, stable asthma is not exclusionary.
- 3. Subject has a documented allergy, hypersensitivity, or intolerance to amphetamine or to any excipients in the investigational product.
- 4. Subject has failed to fully respond, based on investigator judgment, to an adequate course of amphetamine therapy.
- 5. Subject has a known family history of sudden cardiac death or ventricular arrhythmia.
- 6. Subject has a blood pressure measurement ≥95th percentile for age, sex, and height at screening (Visit 1) and/or baseline (Visit 2).

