- If >32 days have elapsed since the screening evaluation was completed at Visit 2, then the following evaluations must be repeated at baseline (Visit 2): vital signs, serum pregnancy test, urine drug screen, clinical laboratory evaluations, and ECGs in triplicate. The physical exam will be abbreviated with a review of the following body systems: general appearance, respiratory, and cardiovascular.
- Height and weight will be measured without shoes and with light clothing using a calibrated stadiometer for height and calibrated scale for weight.

Study Protocol SHP465-309

07 September 2017

Page 21

Table 1: Schedule of Assessments

	Screening	g/Washout ^a	Baseline		Follow-up			
Visit Number ^b	1	Phone call	2	3	4	5	6/ET ^c	Phone call
Study Week	-5 to -1	-1	0	1	2	3	4	5
Study Day ^b	-32 to −3	-7	0	7	14	21	28	35

Vital signs include oral or tympanic temperature, pulse, sitting blood pressure, and respiration rate. The subject will have been seated for a minimum of 3 minutes before blood pressure, pulse and respiration rate measurements are taken. Measurement of blood pressure and pulse will be collected 3 times (with approximately 2 minutes in between each collection). The average of each set of 3 measurements will be used to determine continued participation in the study.

Blood pressure and pulse rate will be measured at each study visit. Temperature and sitting respiration rate will be measured at screening (Visit 1) and/or baseline (Visit 2) only.

k For females of child-bearing potential only.

Electrocardiograms will be recorded in triplicate with approximately 3 minutes in between each collection at screening only and at baseline only if >32 days have elapsed since the screening evaluation was completed at Visit 1.

07 September 2017

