1.2 Product Background and Clinical Information

1.2.1 Clinical Information

SHP465 and its prototypes have been evaluated in 1641 subjects in 16 clinical studies, of which 13 clinical studies were in adult subjects aged 18 to 55 years and 3 clinical studies were in pediatric subjects aged 6 to 17 years. The SHP465 clinical development program has shown that doses of 12.5 to 50 mg in adult subjects and 6.25 to 25 mg in pediatric subjects demonstrate a safety and efficacy comparable to the profile reflected in class labeling for stimulant products approved in the United States (US).

The pharmacokinetic (PK) profile of SHP465 is not affected if the capsule is consumed intact or if capsule contents are sprinkled onto a small amount of food (ie, 1 tablespoon of applesauce) and then ingested. The PK properties of SHP465 are not affected by sex or race. The PK properties between d- and l-amphetamine are similar.

07 September 2017

Acceptable safety and tolerability profiles observed were consistent with the types of side effect specified in stimulant class labeling in the US. Specifically, administration of SHP465 was associated with increases in blood pressure (mean increase approximately 2-4 mmHg) and heart rate (mean increase approximately 3-6 bpm), and treatment-emergent adverse events (TEAEs) of insomnia, decreased appetite, decreased weight, heart rate increased, and anxiety, as well as psychiatric events (eg, mania, suicidality).

Always refer to the latest version of the SHP465 IB for the overall risk/benefit assessment and the most accurate and current information regarding the drug metabolism, PK, efficacy, and safety of SHP465.

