3.2 Duration and Study Completion Definition

The subject's duration of participation is expected to be approximately 6-10 weeks. The study will be completed in approximately 7 months.

- Planned duration of screening/washout period: up to 32 days
- Planned duration of treatment period: 4 weeks
- Planned duration of safety follow-up: 1 week

The study completion date is defined as the date the final subject, across all sites, completes their final protocol-defined assessment. Please note that this includes the follow-up visit or contact, whichever is later. The study completion date is used to ascertain timing for study results posting and reporting.

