5.2.2 Prohibited Treatment

Shown in Table 2 are excluded medications for this study. Subjects can only be instructed to discontinue a medication for this study after informed consent has been obtained.

Table 2: Common Excluded Treatments and Associated Washout Period Relative to Baseline Visit (Visit 2)

		Minimum Number of Days Before Baseline Visit			
Treatment	7	14	30		
Psychostimulants, amphetamines, and amphetamine-like agents	X				
Antihypertensives ^a	X				
Antihistamines (centrally and peripherally active)		X			
Herbal preparations (including melatonin)		X			
Sedatives, anxiolytics, antipsychotics ^a			X		
Monoamine oxidase inhibitor ^a			X		
Antidepressants ^a			X		
Clonidine and guanfacine			X		
Selective noradrenaline reuptake inhibitors and noradrenaline reuptake inhibitors ^a			X		
CYP2D6 inhibitors (eg, paroxetine, fluoxetine, quinidine, ritonavir)			X		
Alkalinizing agents (eg, sodium bicarbonate, acetazolamide, some thiazides)			X		
Acidifying agents (eg, guanethidine, reserpine, glutamic acid HCl, ascorbic acid, ammonium chloride, sodium acid phosphate, methenamine salts)			X		

^a These medications may signal that an exclusionary diagnosis is present. The medical monitor should be consulted before instructing a subject to discontinue 1 of these medications for this study.

Page 36

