7.1.1.2 Washout Telephone Call

The washout period should be initiated after clinical laboratory test results and 12-lead ECG results have been received and reviewed by the investigator. Eligible subjects will be contacted by a member of the site staff and provided with instructions on discontinuing any protocol-prohibited medications.

During washout, a subject's current prohibited medications (if applicable) will be discontinued for a period of a minimum of 5 times the half-life of the medication. Washout periods for prohibited medications are defined in Table 2.

As part of the washout telephone call, site personnel should perform the following procedures.

- Schedule the baseline visit (Visit 2).
- Review the inclusion/exclusion criteria.
- Ask about any concomitant medications that the subject is taking. If new concomitant
 medications that require washout are noted, instructions for appropriate washout should be
 provided.
- Provide instructions on discontinuing any medication requiring washout.
- Determine if any AEs have occurred since the screening visit (Visit 1).

If a medication washout is not necessary, the washout telephone call will include all the above procedures except providing instructions on discontinuing any current medications and must occur prior to the baseline visit.

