7.2.4.8 Electrocardiogram

A 12-lead ECG will be performed at the screening visit (Visit 1), Visit 4, and Visit 6/ET. At screening, 3 ECGs taken approximately 3 minutes apart will be collected; if >32 days have passed since screening, these ECGS will be collected in triplicate at Visit (Visit 2) to ensure appropriate baseline intervals are established. Additional ECGs may be performed during the study at the investigator's discretion.

Page 52

07 September 2017

All ECGs will be performed after 3 minutes of rest using the central ECG provider's equipment and will be sent to the central ECG provider electronically.

The initial interpretation of the ECG, normal or abnormal and clinical significance, will be performed immediately after collection to ensure the safety of each subject. An ECG tracing will then be evaluated by a cardiologist at a central ECG reading vendor and returned to the site with a determination of normal or abnormal. Upon review of the report from this vendor, the investigator will re-evaluate the clinical significance of the ECG while taking into consideration all other safety data available for the subject.

Although a central ECG reader is being used for this study, the eligibility of the subject is based on the investigator's assessment of the ECG. If abnormal and significant results are observed following assessment by the central reader, the investigator, in consultation with the appointed CRO medical monitor, reconfirms subject eligibility to continue.

All ECGs transmitted to the central ECG reader will be analyzed. If the central ECG reader receives multiple ECGs, the first readable ECGs will be analyzed as the scheduled ECG. Every ECG transmitted to the central ECG reader will have corresponding source document data collected. No ECG should be deleted by study site personnel. All ECGs must be transmitted to the central provider regardless of quality, results, or number of ECGs taken at a respective visit.

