12.4 Electrocardiogram (ECG)

Electrocardiogram results and change from baseline will be summarized at each visit and at the FoTA by treatment group. If there are multiple assessments for the interpretation at any visit, the worst interpretation will be used in the summary tables. For the interval parameters at post-baseline visits, the first readable result will be used if there are multiple assessments.

For the ECG interval parameters, baseline is defined as the average of all valid ECG measurements as the last assessment obtained prior to the first dose of the investigational product. For the ECG interpretation, baseline will be the ECG with the worst interpretation obtained at the baseline Visit (Visit 2), providing this is prior to the first dose of the investigational product.

PCI criteria will be applied to all ECG data at each visit including any repeat/unscheduled assessments and presented by visit and treatment group. PCI criteria are defined in Table 7.

Table 7 Cr	riteria for Potent	ially Clinically	/ Important ECG Valu	ues
------------	--------------------	------------------	----------------------	-----

ECG Parameter	Outlier Criteria
ECG result	Shift from a normal baseline to an abnormal finding or from
	an abnormal baseline to a new abnormal finding
Heart rate	≤50 beats/minute* or ≥100 beats/minute*
PR interval (increase)	≥200 msec*
QRS interval	≥120 msec*
QTcF/QTcB	≥450 msec* and <480 msec*
	≥480 msec* and <500 msec*
	≥ 500msec*
QT/QTc from Baseline	≥30 msec* and <60 msec*
	≥60 msec*

^{*}The NCI has not specified a value, Shire physicians have agreed on values provided. ECG=electrocardiogram; QTcB=Bazett's corrected QT interval; QTcF=Fridericia's corrected QT interval

is the total number of subjects with at least 1 PCI post-baseline ECG value.

The number and percentage of subjects with post-baseline PCI values will be tabulated. The percentages for the observed value criteria will be calculated relative to the number of subjects with at least 1 post-baseline assessment available per parameter and visit. The percentages for the change from baseline criteria will be calculated relative to the number of subjects with available baseline and at least 1 post-baseline assessment per parameter and visit. The numerator

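### For children on a stimulant at entry, the only routine pre-dose ECG precedes washout, so within-arm ECG heart-rate change mixes stopping the old drug with the study treatment

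*Protocol*

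**What the plan says.** **Entry.** Treated children are eligible. Synopsis inclusion criterion 8 reads "Subject is currently not on ADHD therapy, or is not completely satisfied with any aspect of their current ADHD therapy", and Section 4.1 criterion 9 is similar. Exclusion 20 makes an exception for a current ADHD stimulant on the urine drug screen.

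**Washout.** Protocol Section 7.1.1.2 says "The washout period should be initiated after clinical laboratory test results and 12-lead ECG results have been received and reviewed by the investigator". In Table 2 (Section 5.2.2) the row "Psychostimulants, amphetamines, and amphetamine-like agents" is marked in the 7-day column, the shortest minimum interval before Visit 2.

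**ECG schedule.** Section 7.2.4.8 says "A 12-lead ECG will be performed at the screening visit (Visit 1), Visit 4, and Visit 6/ET". The ECG footnote to the Schedule of Assessments requires triplicates "at screening only and at baseline only if >32 days have elapsed since the screening evaluation was completed at Visit 1". Section 3.2 gives "Planned duration of screening/washout period: up to 32 days", so the repeat applies only when the planned window has been overrun.

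**Analysis.** For interval parameters, SAP 12.4 states that "baseline is defined as the average of all valid ECG measurements as the last assessment obtained prior to the first dose of the investigational product". ECG results and change from baseline are summarized by treatment group at each visit and at the final on-treatment assessment (FoTA). In SAP Table 7 the heart-rate, PR, QRS and QTc-level criteria are absolute. The QT/QTc criteria of 30 to below 60 msec and of 60 msec or more are changes from baseline.

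**The concern.** A baseline is meant to show the child's state without active drug. For a child on a stimulant at entry, the baseline ECG comes before washout, whereas the Visit 4 and Visit 6 ECGs come after washout and on study treatment. The change therefore has two components: loss of the old stimulant's effect, and any effect of the allocated treatment. If the old stimulant raised heart rate, the SHP465 arm shows too small a rise and the placebo arm shows a fall that placebo did not cause.

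The SAP neither flags this nor plans a between-arm ECG contrast, so a reader is left with the two within-arm columns. The vital-sign pulse tables use a Visit 2 baseline taken after washout. Pulse and ECG heart rate could then show different changes in the same children, with nothing in the report to explain why. ECG findings are named in the safety objective, and heart rate is one of the effects the protocol itself attributes to SHP465.

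**Working it through.** The plan states no figure for this point, so there is none to reproduce. The check is the visit order, followed by expected changes.

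**Order of events for an on-schedule stimulant user**
1. Consent and Visit 1 ECG, with the child still on the stimulant
2. ECG reviewed, then washout of at least 7 days
3. Visit 2 with no ECG, because 32 days or fewer have passed
4. First dose the next morning
5. ECG at Visits 4 and 6

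The last pre-dose ECG is the one in step 1.

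**Inputs**
- *e*, heart-rate rise on SHP465: 3-6 bpm (Protocol 1.2.1, across the whole development programme)
- *p*, rise from the prior stimulant: not given; assumed equal to *e*
- *s*, share on a stimulant at the baseline ECG: not given; assumed 25-75%
- Children per arm: 60/2 = 30 (1:1 randomization)

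**Expected change from baseline**
- SHP465: e - s·p
- Placebo: -s·p
- Difference: (e - s·p) - (-s·p) = e

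| s | p = e = 3 bpm: SHP465 / placebo / difference | p = e = 6 bpm: SHP465 / placebo / difference |
|---|---|---|
| 25% | +2.25 / -0.75 / 3 | +4.5 / -1.5 / 6 |
| 50% | +1.5 / -1.5 / 3 | +3.0 / -3.0 / 6 |
| 75% | +0.75 / -2.25 / 3 | +1.5 / -4.5 / 6 |

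With a drug-free baseline (s·p = 0) the arms would show +3 to +6 and 0. The difference is the same in every row.

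**Chance imbalance in prior use.** Randomization is stratified by age group only. The SD of the resulting shift in the between-arm difference is p·√(2s(1-s)/30):
- Smallest: 3 × √(2 × 0.25 × 0.75/30) = 3 × 0.112 = 0.34 bpm
- Largest: 6 × √(2 × 0.5 × 0.5/30) = 6 × 0.129 = 0.77 bpm

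**QT and QTc.** Section 1.2.1 reports blood-pressure and heart-rate increases and gives no QT figure. For illustration, assume QTcF stays at 400 msec while withdrawal lowers heart rate from 81 to 75 bpm. With RR = 60/heart rate, RR goes from 0.741 to 0.800 s.
- QTcF: no change, by assumption
- QTcB = 400 × RR^(-1/6): 420.5 to 415.2, a fall of about 5.4 msec
- Uncorrected QT = 400 × RR^(1/3): 361.9 to 371.3, a rise of about 9.4 msec

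Even with one set of assumptions the sign depends on the measure, and both shifts are well below 30 msec.

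**The case against.** The strongest reply is that this is a randomized placebo-controlled trial, so the drug effect is the between-arm difference, and that difference is not biased in expectation. This stands. A reader might infer that the trial will understate the cardiac effect of SHP465; the algebra above shows that it will not. Only the within-arm means and change-based counts are affected.

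A reader might also infer that QTc change is understated on SHP465 and falls falsely on placebo. The documents support neither direction nor size.

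The size is soft. The proportion of the SHP465 rise that disappears is simply *s* when p = e, so 25-75% repeats an assumption. The 3-6 bpm is not specific to 6.25 mg in children, and applying it to any prior stimulant is a further assumption. The documents do not say whether a dose was taken on the day of the Visit 1 ECG. Discretionary ECGs are allowed, and some children will pass 32 days. These points could shrink the bias, but none removes it for an on-schedule child who took the stimulant.

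Chance imbalance is minor. If the SD of heart-rate change is 10-12 bpm (assumption), the standard error of the arm difference is 10 × √(2/30) = 2.6 to 12 × √(2/30) = 3.1 bpm. Adding 0.77 in quadrature raises it by about 3-4%.

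Part of the remedy is already in place. Pulse has a post-washout baseline (SAP 12.3), observed ECG results are tabulated by arm, and ADHD medication history is summarized by arm (SAP 10).

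Finally, one might suppose that children with a 30-day washout escape because they will usually need the repeat ECG. That is not shown: 30 days plus the ECG review time exceeds 32 only if review takes more than 2 days, and the protocol does not state a review time.

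**Conclusion.** The point holds for within-arm ECG heart-rate change in children on a stimulant at entry. Under the two stated assumptions (25-75% of children on a stimulant, prior-drug effect of 3-6 bpm), the SHP465 arm would show about +0.75 to +4.5 bpm instead of +3 to +6, and placebo about -0.75 to -4.5 instead of 0. The visit order and baseline definition come from the documents; the size does not, and it scales with s·p.

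The absolute limits for potentially clinically important values are unaffected. QT/QTc change and its 30 and 60 msec counts may be confounded in an unknown direction and by an unknown amount. The ECG analyses are descriptive, so no efficacy conclusion or Type I error rate is involved. This is a modest flaw in interpretability that is cheap to correct in the SAP. It does not make an added Visit 2 ECG necessary: that would be a new procedure, and a post-washout pulse change is already available.

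**What to change.** In SAP 12.4:
- Present ECG change from baseline, and the change-based counts of potentially clinically important values, separately for children on and off ADHD medication at the baseline ECG. The status can be derived from medication data already collected.
- Report the SHP465-placebo difference in ECG values at Visit 4, Visit 6 and FoTA, and name it as the measure of drug effect.
- Footnote the within-arm change tables to say that the baseline ECG may precede washout.

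The cost is one extra table split and one added contrast, with no new data. The strata will be small: at a 25% share, 0.25 × 30 gives about 7 children per arm on medication, so rare change-based counts there will say little. Differences in observed values do not use baseline and may be less precise than differences in change.

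The same edit should reconcile the interpretation baseline in SAP 12.4, which is taken from a Visit 2 ECG that on-schedule children are not required to have.

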1 BACKGROUND INFORMATION

SHP465 extended-release capsules contain mixed salts of a single-entity amphetamine, a CNS stimulant. The product was previously referred to as SPD465 however it is now being studied under the code of SHP465. SHP465 contains equal amounts (by weight) of 4 salts: dextroamphetamine sulfate and amphetamine sulfate, dextroamphetamine saccharate and amphetamine aspartate monohydrate. This results in a 3:1 mixture of dextro- to levo- amphetamine base equivalent.

SHP465 capsules are for oral administration. They contain 3 types of drug-releasing beads, an immediate release and 2 different types of delayed release (DR) beads. The first DR bead releases amphetamine at pH 5.5 and the other DR bead releases amphetamine at pH 7.0.

Amphetamines are noncatecholamine sympathomimetic amines with central nervous system stimulant activity. Amphetamine increases the availability of biogenic amines (primarily dopamine and norepinephrine) in central nerve terminals through multiple actions, including stimulating neurotransmitter release into the nerve terminal and inhibiting reuptake from the synapse. These actions may be the basis of its therapeutic actions in ADHD; however, the mode of therapeutic action in ADHD is not known.

Additional information can be found in the current Investigator's Brochure (IB) for SHP465.

1.1 **Indication and Current Treatment Options**

Attention-deficit/hyperactivity disorder is a psychiatric disorder characterized by developmentally inappropriate degrees of inattentiveness, impulsivity, and hyperactivity. Although ADHD is the most common neurodevelopmental disorder of childhood (Rowland et al. 2002) and it has been extensively studied in young children, ADHD occurs in all age groups (Brown 2000).

Prevalence estimates of ADHD in school-age children have ranged from 2-18% in community samples (Rowland et al. 2002; Centers for Disease Control and Prevention 2005). The Diagnostic and Statistical Manual of Mental Disorders, Fourth Edition – Text Revision® estimates that the disorder is prevalent in 3-7% of school-age children (American Psychiatric Association 2000). An analysis of data from the National Survey of Children's Health performed by the Centers for Disease Control and Prevention (2005) estimates that 7.8% of children aged 4-17 years have been diagnosed with the disorder in the US as of 2003.

Although ADHD was initially believed to be predominantly a childhood disorder, the advent of consensus diagnostic criteria for ADHD along with more rigorous prospective research has documented the persistence of this disorder into adolescence in up to 70% and into adulthood in up to 66% of childhood cases (Mannuzza et al. 1998; Barkley 1998; Zametkin and Ernst 1999). Despite the prevalence of ADHD in all age groups, the majority of studies have been done in children and adults.

SHP465-309

07 September 2017

A review of available literature indicates that psychostimulants are efficacious in treating adolescents as well as the treatment for younger children with ADHD (Biederman et al. 1996; Findling et al. 2001).

The 3 main symptoms of ADHD are inattention, hyperactivity, and impulsivity. Symptoms of inattention include difficulty paying attention, making careless mistakes, difficulty organizing tasks, not finishing tasks, not listening, and being forgetful and easily distracted. Symptoms of hyperactivity and impulsivity include fidgeting, running, or moving about when expected to be still, difficulty playing quietly, talking excessively, and interrupting others. Many people have symptoms like these occasionally, but patients with ADHD have these symptoms more often and to a greater extent than others their age. These symptoms must appear before age 7 years, be present for more than 6 months, and must be adversely affecting social, occupational, or school functioning for the diagnosis of ADHD to be made.

The presumed pathophysiology of ADHD is an abnormality in central dopaminergic and noradrenergic tone (Biederman and Spencer 1999). This presumption is based on the discovery that effective pharmacotherapies in children and adults have an impact on these 2 neurotransmitters (Wilens and Spencer 2000; Faraone and Biederman 1998).

Stimulants, including amphetamine and methylphenidate products are currently the most prescribed medications for the treatment of ADHD. Other nonstimulant classes of medications are also approved for the treatment of ADHD including a norepinephrine reuptake inhibitor, STRATTERA® (atomoxetine hydrochloride) and alpha-2-agonists, INTUNIV® (guanfacine hydrochloride) and KAPVAY® (clonidine hydrochloride). However, comprehensive reviews of clinical studies investigating the pharmacotherapy of ADHD clearly demonstrate that stimulant medications (ie, methylphenidate and amphetamine) produce the most robust improvements in symptom expression across age ranges as compared with nonstimulant therapies (Faraone et al. 2006).

